4.0 Study Endpoints

The outcome measures have been chosen to provide the most complete and accurate evaluation of therapy results. Outcome measures are numerous in the voice field, and to allow comparison across studies, the American Speech-Language-Hearing Association (ASHA) has recently developed a recommended protocol for instrumental assessment of voice(36). We modeled our measurement methods on these recommendations and added supplementary outcomes relevant to this study.

Voice measures. [Note: voice measurements will be obtained from the participants' standard of care voice assessments]

Videostroboscopy: Recordings of vocal fold vibration from sustained phonations of /i/ at various pitch and loudness levels will be used 1) to assess the parameters described in the Voice-Vibratory Assessment with Laryngeal Imaging (VALI) rating form(37), and 2) for measurements of normalized glottal gap (NGG)(38).

Acoustic measures: The Computerized Speech Lab (CSL) is used to record sustained phonation at various pitch and intensity levels, reading of the Consensus Auditory-Perceptual Evaluation of Voice (CAPE-V)(40) sentences, as well as a short natural conversation with the SLP. Acoustic analysis will include: 1) measures of voice intensity: habitual and maximum sound pressure levels (SPL); 2) measures of fundamental

frequency (F0): mean, minimum, and maximum vocal F0, and 3) measures of voice quality: cepstral peak, jitter, shimmer, and harmonics-to-noise ratio.

Perceptual judgments of voice quality: The CAPE-V(40) rating form will be used for the judgment of voice quality of sustained phonation, reading and conversational speech tasks recorded via CSL. The CAPE-V form includes ratings of overall severity, roughness, breathiness, strain, pitch, and loudness, as well as qualitative information about resonance and additional features.

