10.0 Study Design / Methods

Overview

After being enrolled in the study, treatment-seeking patients with a diagnosis of presbyphonia will undergo baseline respiratory assessments including spirometry and respiratory muscle strength measures as well as voice recordings (acoustic assessments). Participants will then be blocked-randomized (based on their MIP and MEP) to one of three groups using a 3-parallel arm design: (2 experimental groups and 1 control group), using a 3-parallel arm design: 1) inspiratory training (IMST) (experimental group), 2) expiratory training (EMST) (experimental group), or 3) standard of care (VFE) (control group), delivered four times (see table 1 for participant timeline). The sessions will occur on the same days as the participants' scheduled voice therapy sessions when possible. Participants will be asked to practice their respective exercises for 10 minutes, twice daily, seven days a week during the duration of the study. A final assessment session, after the 4th therapy session, will mirror the baseline measures. Participants will receive a monetary compensation of \$20 for each study visit, for a maximum of \$80 for the whole study. Payments will be made via cash. Outcomes that rely on subjective judgment (visual ratings of

videostroboscopy and perceptual judgments of voice quality) will be rated by trained judges (SLPs) blinded to the group assignment. [**Note**: Long-term follow-up will not be conducted. This study's focus is on the mechanistic effects of the intervention; future studies, given positive outcomes from this study, will explore the effectiveness and long-term effects.]

Table 1: Participant Timeline

Visit 1	Visit 2	Visit 3	Visit 4
Baseline assessment session			
Therapy session 1	Therapy session 2	Therapy session 3	Therapy session 4
			Final assessment session

Patient Participants

Standard of Care Assessments (Procedures being performed already for diagnostic purposes)

- Laryngeal imaging: prior to the examination, the laryngologist will administer topical lidocaine and neosynepherine in a spray to one of the nasal cavities. The laryngologist then passes the camera through the nose to examine the vocal folds. The participant will be asked to sustain phonation on the vowel /i/ for at least 3 seconds and to repeat with pitch and loudness variations.

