Firstly, the medical chart of the participant will be reviewed to obtain the following information: height and weight. This information will be used to perform the respiratory and muscle pressure assessments. The medical chart will also be used to track the speech therapy appointments, since research visits will take place on the same days. Spirometry assessments will take place at baseline and after the fourth intervention session. Muscle pressure testing and acoustic assessments will be conducted at baseline and before and after each intervention session.

Spirometry: Prior to the tasks, the participant will put on a nose clip and make sure that the lips are well sealed around the tube with no air is escaping. They will be asked to breathe normally, and then take a full inspiration and blow out with force during at least 6 seconds, in the spirometer. Those maneuvers will be repeated at least three times, to verify test reliability. No more than eight repetitions should be needed(47). The participant is seated to reduce risks of fall.

• Muscle pressure (maximum inspiratory pressure-MIP- and maximum expiratory pressure-MEP):

- o MIP: the participant is instructed to exhale slowly and completely, seal lips firmly around the mouthpiece, and then breathe in forcefully. The PI will note the largest negative pressure sustained for at least one second on the pressure gauge. The participant will rest for about one minute and then repeat the maneuver up to 4 additional times (with the goal of matching the highest 2 trials within 10 cmH₂O)(48).
- o MEP: the participant is instructed to inhale slowly and completely, seal lips firmly around the mouthpiece, and then breathe out forcefully. The PI will note the largest positive pressure sustained for at least one second on the pressure gauge. The participant will rest for about one minute and then repeat the maneuver up to 4 additional times (with the goal of matching the highest 2 trials within 10 cmH₂O) (48).

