- Acoustic assessment: The microphone is positioned at a 45° angle and at a standardized distance from the mouth of the participant. The participant is asked to sustain phonation on the vowels /a/ and /i/ at a comfortable loudness for 3-5 seconds and as low and as loud as possible, to glide to a high pitch and to a low pitch, and from a soft voice to a loud voice. They are asked to sustain the vowel /a/ for as long as possible. They are then asked to read the 6 CAPE-V sentences and to have a short natural conversation with the speech therapist. The participant is then asked to rate their perceived phonatory effort (PPE) on a scale.
- Self-Assessment questionnaire: the participant will be asked to fill out the Communicative
 Participation Item bank (CPIB) questionnaire, which consists of 10 questions on communication.

Participants will be stratified based on their muscle pressure measures: 1) within normal limits MIP and MEP; 2) preserved MIP and decreased MIP; 3) preserved MEP and decreased MIP; 4) decreased MIP and MEP. This stratification is crucial to the study design because it will ensure an equal repartition of the

different respiratory profiles and deficits across treatment groups. Participants that don't meet stratification requirements will be excluded from the study.

Participants will be blocked-randomized into three groups (allocation ratio 1:1:1): IMST, EMST and VFE (see description of the interventions below).

Experimental Interventions (Procedures to be performed solely as part of this research study):

Participants in all groups will attend four sessions with a study team member. Intervention sessions will last approximately 30-45 minutes each. Each session will include pre- and post-treatment muscle pressure and acoustic measurements.

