12.0 Data Management

Data Analysis Plan

Demographic characteristics will be compared across the 3 intervention groups, using a RxC contingency table method for categorical variables (gender, smoking history, voice use, racial and ethnic category) and a one-way ANOVA for continuous variables (age, weight, height). Baseline characteristics will be compared across the 3 intervention groups using a Kruskal-Wallis one-way analysis of variance by ranks for ordinal data (GFI, RSI, and VHI scores), a RxC contingency table for categorical variables (glottal gap shape, free edge contour, vertical level, phase closure) and a one-way ANOVA for continuous variables. Aim 1: To assess the effects of respiratory training on voice and respiratory outcomes in patients with presbyphonia. Data will be analyzed on an intention-to-treat basis using multifactor repeated measures generalized linear regression. Distributional assessment will be made for each outcome to confirm optimal distributional assignment and potential need for outcome transformation (i.e. log link). In the model, the repeated factor is time, which has two levels (pre- or post-intervention) and the independent factor is the intervention, which has three levels (IMST, EMST, VFE). In the case of a significant between-subjects effect, multiple comparison tests will be conducted to determine which groups differ. The post-hoc analysis will be done using Tukey's honestly significant difference (offering protection against type I error without being too conservative). Spearman and Person correlations will be calculated to establish inter and intrarater reliability. Aim 2: To identify profiles of presbyphonic patients that would benefit the most from respiratory training. Logistic regression will be conducted to predict which patients improved following inspiratory training and which patients improved following expiratory training, based on their baseline clinical characteristics. Two outcome variables will be indicative of meaningful clinical improvement: 1) MPT (to measure function), and 2) GFI (to measure patient perception of function). Meaningful clinical improvement will be defined by an increase of at least 4 seconds in MPT or a decrease of at least 4 points in GFI score. Participants will be dichotomized as having meaningful clinical improvement, or not, based on these outcomes. Predictors will include MIP, MEP, maximum SPL, breaths per minute, FVC, FEV1, and P_s. These measures were chosen because they are directly influenced by the integrity of the respiratory system.

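### The Aim 1 model compares change scores between two time points, with no baseline adjustment or randomisation stratum, and leaves the per-session MIP, MEP and MPT values unused

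*Combined protocol and SAP*

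**What the plan says.** Section 12.0 (Data Analysis Plan, Aim 1) states: "Data will be analyzed on an intention-to-treat basis using multifactor repeated measures generalized linear regression". It names two factors, intervention with three levels and time, and says that "the repeated factor is time, which has two levels (pre- or post-intervention". It mentions no baseline covariate, no baseline constraint, no stratum and no rule for missing outcomes.

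Section 10.0 schedules far more data for some outcomes: "Muscle pressure testing and acoustic assessments will be conducted at baseline and before and after each intervention session". It repeats this under Experimental Interventions: "Each session will include pre- and post-treatment muscle pressure and acoustic measurements". The study's acoustic protocol includes MPT: "They are asked to sustain the vowel /a/ for as long as possible". MPT is also the outcome used in the Sample Size Justification. Spirometry differs: "Spirometry assessments will take place at baseline and after the fourth intervention session".

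Two passages blur the schedule. Table 1 lists the "Baseline assessment session" and therapy session 1 under the same Visit 1. Section 4.0 notes that "voice measurements will be obtained from the participants' standard of care voice assessments", whereas Section 10.0 makes MPT a study measurement at each session.

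Section 10.0 also stratifies participants by MIP and MEP profile before block randomisation.

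**The concern.** The Aim 1 hypotheses concern greater improvement. In a model with arm and two-level time, that question is answered by the arm-by-time contrast. With baseline means free in each arm, this contrast is the difference between arms in mean change from one baseline value to one final value. Randomisation makes the true baseline means equal across arms, and a change score makes no use of that fact. Unless the correlation is close to 1, it is less precise than a baseline-adjusted comparison. Omitting the stratum also ignores a design factor that should predict MIP and MEP.

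MIP, MEP and MPT are scheduled on up to nine occasions (baseline, plus before and after each of four sessions, the last coinciding with the final assessment), and Aim 1 uses two. No other analysis in the plan uses the rest. If someone leaves after visit 2 or 3, their post-baseline values cannot enter the model, although the analysis is described as intention-to-treat. With 16 per arm, avoidable loss of precision matters. If use of the interim data is left open, occasions could also be chosen after the results are seen.

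**Working it through.** **The plan's nearest figure.** The plan gives no variance or correlation for Aim 1. Its sample size is n = 2(z₀.₉₅ + z₀.₈₀)²/d² with d = 0.90 and alpha 0.10, taken as two-sided because sidedness is not stated. This gives 15.27 per group against the stated 15. Power at 15 is 79.4% by the normal approximation and 77.6% by the t-test. The stated figure therefore reproduces closely, and the point below does not depend on any error in it.

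**Inputs.** 16 per arm and 10% dropout (Section 12.0, Sample Size Justification) leave 16 × 0.9 = 14.4 completers. For the calculation, 0.8 per arm leave after visit 2 and 0.8 after visit 3. The within-patient correlation ρ is an assumption, 0.5 to 0.8, equal between all visits.

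**Step 1: baseline constraint alone, two planned time points.** In units of the outcome variance, per participant:
- change score: 2(1 − ρ)
- baseline-constrained or baseline-adjusted: 1 − ρ²
- ratio: (1 − ρ²)/[2(1 − ρ)] = (1 + ρ)/2, which is 0.75 at ρ = 0.5 and 0.90 at ρ = 0.8

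This is a cut of 10-25%. It equals running the change-score analysis with 14.4/0.90 = 16.0 to 14.4/0.75 = 19.2 completers per arm.

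**Step 2: add interim visits and a possible second baseline.** Generalised least squares, with a common baseline mean and free post-baseline means by arm. Entries are the variance of the final-assessment difference relative to the change score among completers.

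| Model | ρ = 0.5 | 0.6 | 0.7 | 0.8 |
|---|---|---|---|---|
| Baseline constrained, two time points | 0.750 | 0.800 | 0.850 | 0.900 |
| + pre-session values, visits 2-4 | 0.739 | 0.786 | 0.832 | 0.879 |
| + second baseline, correlated 0.9 with the first | 0.727 | 0.764 | 0.793 | 0.801 |
| + second baseline, correlated only ρ with the first | 0.661 | 0.681 | 0.698 | 0.713 |

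The cuts are 12-26% in the second row, 20-27% in the third and 29-34% in the fourth.

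**Step 3: what the interim visits add.** 0.739/0.750 = 0.985 and 0.879/0.900 = 0.977, a gain of about 2%. If leaving is also possible after visit 1, the gain is nearer 1%.

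**Step 4: early leavers' baselines.** If the two-level model is fitted by likelihood, leavers' baseline rows stay in. The variance is then (1 − ρ²)/14.4 + (1 − ρ)²/16, compared with 2(1 − ρ)/14.4 among completers:
- ρ = 0.5: (0.0521 + 0.0156)/0.0694 = 0.975
- ρ = 0.8: (0.0250 + 0.0025)/0.0278 = 0.990

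Against that comparator, the Step 1 cut is 1 − 0.75/0.975 = 23% down to 1 − 0.90/0.990 = 9%. The other cuts also shrink by at most about two percentage points.

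**The case against.** A pre/post contrast is a legitimate, simple choice for a 48-person feasibility and mechanistic study. It fits spirometry and the rated outcomes, which are taken only before and after. The interim visits save almost no variance at 10% dropout (about 5 of 48 people), and no bias has been shown. All of this stands. It limits the point to precision and prespecification, and it shows that baseline adjustment matters more than the extra visits.

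Three stronger readings are tempting, and the documents do not support them.

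- **That a second baseline is certainly collected and thrown away, worth 29-34%.** The schedule's wording allows it. Table 1, however, puts baseline and session 1 at one visit, so the pre-session-1 value may be the baseline itself or a same-day repeat. The 29-34% also requires two same-visit values to be no more alike than values from different visits. And the baseline constraint alone supplies 25 of the 34 points at ρ = 0.5 and 10 of the 29 at ρ = 0.8.
- **That all data from early leavers are discarded and the analysis is of completers only.** The plan does not say so. A likelihood or estimating-equation fit keeps their baseline rows, though these add little (Step 4). What is missing is a stated rule for missing outcomes.
- **That the trial is shown to be underpowered.** The stated 15 per group reproduces closely, so this point gives no ground for that claim.

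**Conclusion.** The point holds as one of efficiency and prespecification. As written, the Aim 1 arm-by-time contrast is a change score that ignores the randomisation stratum, and the repeated MIP, MEP and MPT values have no place in any analysis. Relative to a change score, the variance of the final difference falls by about 10-25% from the baseline constraint, about 12-26% with the interim visits, and about 20-27% if a distinct same-visit second baseline correlated 0.9 exists. These figures rest on an assumed correlation of 0.5-0.8, equal between visits, and on 10% dropout shared equally across arms. They exclude any gain from the stratum, for which the documents give no basis.

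The case for the interim visits is mainly one of validity. If leaving relates to earlier measured response, conditioning on those values makes missing at random more plausible. The variance gain is only about 1-2%.

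**What to change.** In Section 12.0, Aim 1:

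- **MPT, MIP and MEP:** use a mixed model with baseline constrained equal across arms and the MIP/MEP randomisation stratum as a factor. The repeated outcomes are the pre-session values at visits 2-4 and the final assessment after session 4. The estimate is the arm difference at that final assessment. Name the covariance structure and a fallback.
- **Spirometry and other pre/post outcomes:** keep the two time points and adjust for baseline and stratum.
- **Second baseline:** state whether the pre-session-1 value is distinct from baseline. If it is, average the two as the baseline and do not also use it as an outcome.
- **Missing data and unused values:** state the missing-at-random assumption, and say what is done with the post-session values at visits 1-3.
- **Reconcile:** the source of MPT (Section 4.0 against Section 10.0), and the second stratum in Section 10.0, which names MIP as both preserved and decreased and must be settled before the stratum can be coded.

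The cost is SAP wording and a little more programming. No new data are needed, and the endpoint stays at the planned assessment after session 4.

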Specific Aim 1: To measure the effects of respiratory training on respiratory and voice outcomes in patients with presbyphonia. Hypothesis 1: The respiratory training groups (inspiratory and/or expiratory) will demonstrate greater improvement in respiratory outcomes, measured through pulmonary function tests and respiratory pressure measures, compared with the voice exercises-only group. Hypothesis 2: The respiratory training groups (inspiratory and/or expiratory) will demonstrate greater improvement in voice-related outcomes than the voice exercises-only group.

Secondary Aim 1: To assess the reliability of the ratings for subjective outcomes (videostroboscopy ratings and perceptual judgements of voice quality). Hypothesis 1: Intra-judge reliability will be of at least 80%. Hypothesis 2: Inter-judge reliability will be of at least 70%.

Specific Aim 2: To determine how baseline measures of respiratory function influence the effects of respiratory training (respiratory and voice outcomes). Hypothesis 1: inspiratory training will have maximal effect on patients with decreased maximum inspiratory pressure (MIP). Hypothesis 2: Expiratory will have maximal effect on patients with decreased maximum expiratory pressure (MEP).

This is an initial feasibility and mechanistic study that has the potential to reveal that respiratory training can significantly improve outcomes from voice therapy by acting in synergy with voice exercises. Currently,

much time is spent in voice therapy on subthreshold 'breathing exercises' that lack evidence. This project will provide guidance for evidence-based and theory driven approaches to leverage respiratory function to improve voice therapy. Conversely, negative findings from this study would indicate that respiratory function is ineffective and not a viable target for therapy in this patient population.

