
Sample Size Justification

We considered maximum phonation time (MPT) as the primary outcome measure for sample size calculation. This measure was chosen because 1) low MPT is a hallmark of patients with presbyphonia, and 2) MPT is directly affected by both the laryngeal and respiratory systems. To estimate the expected effect size between VFE and the I+IVFE and E+VFE groups, we considered MPT values from groups of an

elderly population with different glottal closure and spirometry profiles (49). Considering that a combined intervention (inspiratory or expiratory training combined with voice therapy) would address both laryngeal and respiratory deficits, and that a voice therapy-only intervention would directly address only the laryngeal deficits, we compared MPT between the no-deficit group (complete glottal closure and normal spirometry) and the respiratory-deficit group (complete glottal closure and altered spirometry)(49). Based on these values and the pooled standard deviations, the expected difference between our control and experimental groups would represent a large effect size. As for the withinsubjects effect, a study by Nam et al.(50) found a 33% increase in MPT following a respiratory training intervention program in young adult singers. This corresponds to a very large within-subjects effect size with values of d exceeding 1.2. For Aim 2, we will assess improvement in 2 ways: function (a MPT increase of 4 seconds, which has been associated with a positive perceived effect following voice therapy in older adults(51)) and patient perception of function (a Glottal Function Index (GFI) score decrease of 4 points). An increase of 4 seconds in MPT and a decrease of 4 points on the GFI instrument both correspond to medium-large effect sizes considering the reported standard deviations of these measures in older subjects and in patients with glottal insufficiency (5.1 and 4.5, respectively) (42, 52). Based on the reported studies, the expected effect size for within-subjects and between-subjects differences was set at d=0.90. To have an 80% power to detect an effect size of d=0.90 with an alpha of 0.1 (since this is a pilot study), 15 participants are needed in each group. To account for loss to follow-up (estimated 10% dropouts rate), up to 16 participants will be recruited for each group, 48 patients total.

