The paucity of evidence supporting the therapeutic benefit of respiratory training for patients with voice disorders is concerning considering their widespread use by speech language pathologists (SLPs) (58, 59). Despite the well documented relationship between the respiratory and laryngeal systems, evidence-based guidelines for respiratory training are non-existent in the field of voice therapy. This void represents a critical barrier to optimal care for patients with voice disorders, especially for patients with presbyphonia who have known respiratory declines due to aging.

Current breathing exercises used by SLPs, such as diaphragmatic breathing, increasing extent of thoracic expansion, and increasing period of expiratory airflow on phonemes /s, z, a, æ, i/(29, 60) have not been tested in clinical trials with voice patients. It is likely that most of these exercises are not adequately intensive, in terms of loading, to induce neuromuscular and hypertrophic changes necessary for improving

respiratory muscle strength. Despite this lack of evidence, many clinicians devote substantial time in their therapy sessions to these 'breathing exercises'. In-person therapy time with a SLP is already limited and therefore should not be spent on subthreshold 'breathing exercises', such as diaphragmatic breathing, that lack evidence. If respiratory training does improve function, it would give clinicians an alternative modality to substitute for less evidenced 'exercises' and change current practice by encouraging SLPs to administer an evidence-based respiratory training. In addition, results from this study would allow to identify profiles of patients likely to benefit from respiratory and more precisely from inspiratory or expiratory training, further promoting efficient and impairment-specific allocation of therapy time.

Conversely, negative findings from this study would raise questions about the relevance of respiratory training in patients with presbyphonia and help focus research as well as clinical practice on more effective treatment approaches. If adequately rigorous respiratory training does not produce sufficient improvement in vocal function, it would be a mandate to stop wasting treatment time on subthreshold 'breathing exercises'.

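### Aim 1 tests for a between-subjects effect, which in its usual sense compares pre/post averages, while both hypotheses concern greater improvement; no intervention-by-time contrast is named

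*Combined protocol and SAP*

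**What the plan says.** Section 1.0 (Specific Aim 1) frames both hypotheses as a difference in improvement. For voice outcomes: "The respiratory training groups (inspiratory and/or expiratory) will demonstrate greater improvement in voice-related outcomes than the voice exercises-only group". The hypothesis for respiratory outcomes has the same form.

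Section 12.0 (Data Analysis Plan, Aim 1) sets the model: "Data will be analyzed on an intention-to-treat basis using multifactor repeated measures generalized linear regression". It then gives the factors: "the repeated factor is time, which has two levels (pre- or post-intervention) and the independent factor is the intervention", with three levels for intervention (IMST, EMST, VFE). The rule for going further is "In the case of a significant between-subjects effect, multiple comparison tests will be conducted to determine which groups differ", and the pairwise method is Tukey's HSD.

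The Sample Size Justification in the same section uses maximum phonation time and states that "the expected effect size for within-subjects and between-subjects differences was set at d=0.90". It asks for 80% power at alpha 0.1 and arrives at 15 participants per group.

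No section names an intervention-by-time term, a change score or a baseline-adjusted comparison. The only treatment interaction mentioned is that of training type with baseline respiratory function (section 1.0), which belongs to Aim 2.

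**The concern.** The hypotheses and the decision rule point at different contrasts. Greater improvement is a difference between arms in pre-to-post change. In a model with time and intervention as factors, that is the interaction of the two. The between-subjects effect, in its standard meaning, is the main effect of group, which compares arms on the mean of the pre and post values. Half of that mean is measured before any training has been given, so it dilutes the treatment effect.

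If the gate does not open, no pairwise comparison is made and the outcome is reported as negative. Section 1.0 would read that strongly: "negative findings from this study would indicate that respiratory function is ineffective and not a viable target for therapy". Section 16.0 is milder: "negative findings from this study would raise questions about the relevance of respiratory training in patients with presbyphonia". In either case a real effect could be dismissed because the wrong term was tested.

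**Working it through.** **Inputs from the documents (section 12.0):** d = 0.90, alpha 0.10, 80% power, 15 evaluable per arm, three arms, two time points.

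**Assumptions, not in the documents:** normal outcome with identity link; SD 1 at both visits; equal expected baselines; the 0.90 SD difference present at the post visit only; pre/post correlation ρ = 0.3, 0.5 or 0.7.

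**Step 1. Reproduce the plan's figure.** The plan does not state which test was used.
- Two groups, two-sided normal approximation: n = 2 × ((1.645 + 0.842)/0.90)² = 15.27. Power at 15 per group is 79.4%.
- Three-arm F test on a contrast carrying the full 0.90 SD (df 2, 42): noncentrality = 15 × Σ(dᵢ − d̄)² = 15 × 0.81 × 2/3 = 8.1, giving 79.8% power. The noncentrality is the same whether one training arm works or both do.

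So 15 per group is consistent with an undiluted arm difference of 0.90 SD.

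**Step 2. Standardise each contrast.**
- Group main effect (pre/post average): the difference is 0.90/2 = 0.45 and the variance is (1+ρ)/2, so d = 0.45/√((1+ρ)/2).
- Intervention by time (change): the difference is 0.90 and the variance is 2(1−ρ), so d = 0.90/√(2(1−ρ)).

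**Step 3. Power at 15 per arm, from the noncentral F (df 2, 42; alpha 0.10).**

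| | ρ = 0.3 | ρ = 0.5 | ρ = 0.7 |
|---|---|---|---|
| Main effect, d | 0.56 | 0.52 | 0.49 |
| Main effect, power | 43.8% | 39.6% | 36.3% |
| Interaction, d | 0.76 | 0.90 | 1.16 |
| Interaction, power | 66.5% | 79.8% | 94.6% |
| n per arm for 80%, main effect | 38 | 44 | 50 |
| n per arm for 80%, interaction | 21 | 16 | 10 |

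At ρ = 0 the two tests coincide: 52.7% power, and 30 per arm for 80%. At each positive ρ above, the interaction is the stronger test.

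**Step 4. Follow the whole rule.** Simulation (40,000 runs per ρ) of the F gate followed by Tukey at family alpha 0.10. The chance of showing a given effective training arm better than VFE is 28%, 25% and 22% through the main effect, against 49%, 64% and 85% through the interaction.

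**Step 5. Type I error.** With no effect and ρ from 0 to 0.8, the main effect rejects in 9.9–10.1% of runs and the interaction in 9.8–10.1%. Neither is inflated.

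**The case against.** The best counter-argument is that the authors did not mean the technical term. The Sample Size Justification applies between-subjects differences to an arm-versus-arm contrast at the full d = 0.90, and 15 per group fits an undiluted contrast. A multifactor repeated-measures model is also often fitted with the cross-term, and section 1.0 makes the question clear. This stands as a plausible account of intent. It does not repair the text, because even with the interaction in the model, the gate sentence does not select it. Two analysts could follow the same plan, test different terms and reach opposite conclusions.

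Second, under generalized linear regression the meaning of a group coefficient depends on coding and link. That is true, and the figures above hold only for a normal, identity-link model. But coding does not settle the matter: with the interaction included and baseline as the reference time, the group coefficient is the baseline difference, which randomisation makes zero in expectation. The plan specifies no coding.

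Third, ρ and the scale of d are assumed. If 0.90 is on the change-score scale, gate power becomes 55%, 40% and 26% for ρ = 0.3, 0.5 and 0.7, against 79.8% throughout for the interaction. The size of the loss moves; its direction does not.

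Fourth, naming the interaction does not by itself secure 80%: at ρ = 0.3 it gives 66%. That is correct, and is the reason to allow baseline adjustment. Removing the gate gains almost no power; its merit is simplicity, since Tukey controls the familywise error without it.

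Finally, this is a pilot at alpha 0.1. That tempers the consequences, but section 1.0 still draws a firm conclusion from a negative result.

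**Conclusion.** The concern holds. As written, the Aim 1 decision rule does not test the Aim 1 hypotheses. Taken in its usual sense, the gate would miss a true effect of the planned size more often than it would find it: power is about 36–44% for ρ between 0.7 and 0.3, roughly half the 80% claimed at ρ = 0.5, and 38 to 50 per arm would be needed to restore it. These figures rest on the literal reading, on 15 evaluable per arm, and on a post-only effect of 0.90 SD in a normal outcome. Whether the authors intended that reading cannot be settled from the documents. The sample size of 15 is not faulted here, and false positives are not increased. Because this is the only test stated for the main aim, it should be corrected before analysis.

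**What to change.** Replace the gate sentence in section 12.0 (Data Analysis Plan, Aim 1) with wording such as:

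> Aim 1 will be tested by the intervention-by-time contrast in the repeated-measures model, using the distribution or link chosen for each outcome and the intention-to-treat set. Tukey-adjusted pairwise comparisons of the arms will be based on this contrast and reported with confidence intervals.

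The condition on a significant between-subjects effect should be deleted.

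For continuous outcomes, a baseline-adjusted analysis is an acceptable and more precise option: either a model that constrains baseline means to be equal across arms, or ANCOVA with a stated handling of missing post values. Under the assumptions above, with ANCOVA standardised effect 0.90/√(1−ρ²), omnibus power is about 83%, 89% and 97% at ρ = 0.3, 0.5 and 0.7. It is not required to cure the fault.

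The cost is analysis-plan wording only, with no new data, visits or patients. The planned model, analysis set and Tukey method are kept, and participants with only a baseline value can stay in a likelihood-based fit.
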